The proposed study builds on this successful NIDDK-funded pilot work to address the clear need for a men-tailored approach to diabetes prevention. *Power-Up* is an intervention that is: a) tailored to the needs and preferences of racial/ethnic minority men; b) delivered by men coaches in men-only groups; and c) uses adapted content that highlights issues relevant to men and messaging designed to be acceptable and engaging to men. Based on the pilot results, we propose to conduct a rigorous effectiveness evaluation using a pragmatic RCT design within diverse healthcare settings already implementing standard mixed-gender NDPP. The goals of this study are to: 1) test the effect of *Power-Up* on weight loss; 2) evaluate engagement of men in *Power-Up*; and 3) examine the reach, broader effectiveness, implementation, and costs of *Power-Up* to inform future dissemination efforts and plans for sustainability.

The proposed study will leverage existing collaborations with co-investigators testing best practices for recruitment, implementation and evaluation of NDPP in a bureau of the New York City Department of Health and Mental Hygiene. Through this partnership we will recruit 300 men from across a spectrum of primary care centers - from a major urban academic medical center to small- and medium-sized primary care practices throughout New York City serving disadvantaged communities. Electronic Health Record data will facilitate outreach to the population of eligible men, based on NDPP criteria, rather than relying on physician referral, and will establish a valid denominator for the total population of eligible men, allowing for a rigorous assessment of the reach of our recruitment approach and an evaluation of the representativeness of our sample. Indicators of effectiveness, adoption, implementation and cost will be analyzed, guided by the RE-AIM framework.

Aim 1. Assess the effect of *Power-Up* vs. NDPP on weight loss among racial/ethnic minority men at risk for diabetes.

Hypothesis 1 (Primary Outcome): Men randomized to *Power-Up* will achieve significantly greater weight loss at 16-weeks and 1-year than men in the standard care group referred to mixed-gender NDPP classes.

Aim 2. Compare engagement of racial/ethnic minority men at risk for diabetes in *Power-Up* vs. NDPP.

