Each cycle consists of a 16-week core phase to be completed within 6-months () and six-month post-core maintenance phase of 6 sessions (.). The duration of each cycle is 10-12 months. Concurrent with each Power-Up Cycle, a similar number of NDPP sessions will be available for men assigned to the standard care, mixed-gender NDPP condition.

Inclusion Enrollment Report 1

Using an Existing Dataset or Resource* : ☐ Yes ☒ No

Enrollment Location Type* : ☒ Domestic ☐ Foreign

Enrollment Country(ies): USA: UNITED STATES

Enrollment Location(s): Domestic; primary care clinics in NYC

Comments: Entries reflect totals recruited across Montefiore and PCIP/ NYC-DOHMH sites

Planned

Racial Categories	Ethnic Categories				Total
	Not Hispanic or Latino		Hispanic or Latino		
	Female	Male	Female	Male	
American Indian/ Alaska Native	0	3	0	3	6
Asian	0	6	0	5	11
Native Hawaiian or Other Pacific Islander	0	1	0	0	1
Black or African American	0	71	0	62	133
White	0	70	0	63	133
More than One Race	0	5	0	11	16
Total	0	156	0	144	300

Cumulative (Actual)

Racial Categories	Ethnic Categories									Total
	Not Hispanic or Latino			Hispanic or Latino			Unknown/Not Reported Ethnicity			
	Female	Male	Unknown/ Not Reported	Female	Male	Unknown/ Not Reported	Female	Male	Unknown/ Not Reported	
American Indian/ Alaska Native	0	0	0	0	0	0	0	0	0	0
Asian	0	0	0	0	0	0	0	0	0	0
Native Hawaiian or Other Pacific Islander	0	0	0	0	0	0	0	0	0	0
Black or African American	0	0	0	0	0	0	0	0	0	0
White	0	0	0	0	0	0	0	0	0	0
More than One Race	0	0	0	0	0	0	0	0	0	0
Unknown or Not Reported	0	0	0	0	0	0	0	0	0	0
Total	0	0	0	0	0	0	0	0	0	0

PROTECTION OF HUMANSUBJECTS

1. Risks to Human Subjects

1a. Human Subjects Involvement, Characteristics, and Design. We will evaluate our Aims within a healthcare system that is implementing the NDPP as a standard of care via a practical two-arm randomized controlled trial (RCT), where eligible men are randomly assigned to receive either *Power-Up* or standard, mixed-gender NDPP.

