Materials for the study include digitally measured weight (via GSM connected BodyTrace scales), intervention session attendance records, EHR-16 clinical data, survey responses, digital recordings of individual interviews, and focus groups, and fidelity ratings from coaches, as well by the PIs, based on observation of sessions. These materials will be collected using internet connected scales, by telephone or by remote search of EHR systems by staff based at our study offices. *Power-Up* sessions (16 core sessions delivered over 6 months and 8-10 additional maintenance sessions delivered over the subsequent 6 months for a total of 24 sessions over one year) will also be conducted virtually. Participants will be given the sessions digitally or a paper copy will be mailed out to them upon request. All participants will receive activity, food and weight logs by mail. Participants will also receive a handout on applications and action plans. Surveys of validated self-report questionnaires for psychosocial and behavioral variables will be conducted by telephone by study staff at our AECOM and study offices. These surveys will occur at baseline/enrollment (immediately prior to randomization), at approximately 16-weeks (goal to conduct this survey within a window of +/- 1 month of the 16-week intervention session), and 12-months (goal of +/- 1 month of the 12-month final maintenance session). Surveys may also be conducted by phone, where necessary (e.g., meeting a participant who missed a session to collect weight and administering the survey of self-reports in person, via the same procedure of reading the questions and response scales to the participant, as implemented during telephone administration). Study staff and trained coaches will collect and manage all primary data. Study staff will review coach-collected data on weights, heights, and attendance, as well as coach-completed fidelity checklists, for quality assurance, providing immediate feedback through prompt communication with coaches, by phone, text or in-person to address any quality issues. Protocols for qualitative data collection will be finalized with guidance from [name] (Consultant) and recordings and transcripts will be securely stored at our study offices. Daily activities of staff will be managed by an onsite project manager at each study office site. All staff will be trained, overseen and advised by Drs. [name] and [name] (PIs). The control arm weight and attendance data collection of men assigned to standard care NDPP will be supervised by [name] and for PCIP by [name] in collaboration with [name] (PCIP, co-I).

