
The primary outcome measure will be percent change in weight at the end of the Core (16 weekly) sessions and at the end of 12 months. We will examine several process and moderating variables, based on a telephone survey of self-report measures validated for English and Spanish language and in-person and telephonic administration, as well as EHR-extracted clinical variables, such as A1c, blood pressure, lipids, etc. 6 months after the delivery of the final session weights will also be EHR-extracted from clinical visits during the 1-year trial period, the 6 month wait is to allow for the updating of EHR data. Extracting these weights will help us capture weights for those who never attended sessions. Coaches will record , weight (using wireless internet connected scales), session attendance logs via study- ID coded and de-identified data entry. They will also complete fidelity checklists. Both of these data entry protocols will be supervised for quality control by study staff. Staff will also track and keep records of all study- related costs. These records will be reviewed periodically by the project managers of each site and by [name] (Co-I). Through coach surveys, coach interviews and participant individual interviews and focus groups, we will examine perceptions of *Power-Up*, fidelity to the model, barriers and facilitators to implementation and engagement, and recommendations for improvement. Participant identifying information will only be known to the primary study staff. Identifying information will be stored separately from study data in locked file cabinets in our study offices. Data will not be shared between study staff of participating health care systems and de-identified data for *Power-Up* participants will be shared with the *Power-Up* data analyst ([name], Co-I) for analysis.

Potential risks of participation are minimal and include the possibility that some participants may feel uncomfortable answering questions, or talking about their weight, food habits, physical activity, and factors that affect behavior. The intervention does not convey more than minimal risk and there is no reason to suspect that any serious adverse events will be attributable to it. All participants will be strongly encouraged to speak to their health care provider about safe and appropriate levels of exercise, as they would for any change in

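### The first primary weight is set by two clocks, 16 weeks and the end of the Core, and the protocol lets these differ by about 10 weeks

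*Protocol*

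**What the plan says.** Hypothesis 1 (under Aim 1, repeated in section 3 on potential benefits) predicts "significantly greater weight loss at 16-weeks and 1-year". Section 1b, Study Procedures, gives the primary outcome as "percent change in weight at the end of the Core (16 weekly) sessions and at the end of 12 months". The first assessment is thus a calendar time in the hypothesis and a programme milestone in the outcome definition.

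The length of the Core is given in three ways:

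- Outcome definition in section 1b: sixteen weekly sessions.
- Intervention Cycles Timeline: "Each cycle consists of a 16-week core phase to be completed within 6-months".
- Description of the intervention, also in section 1b: "16 core sessions delivered over 6 months and 8-10 additional maintenance sessions delivered over the subsequent 6 months". The same sentence puts the yearly total at 24.

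The Intervention Cycles Timeline adds a "six-month post-core maintenance phase of 6 sessions" and states that "The duration of each cycle is 10-12 months". The Adverse Event Monitoring text also counts six maintenance sessions.

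On collection, Retention Strategies places the weigh-ins at designated sessions labelled 16 weeks and 12 months. Section 1b says weights are measured primarily at sessions, with additional procedures for men who do not attend. It also provides for extracting weights from clinical visits in the trial year. For the control arm, the Intervention Cycles Timeline says that a similar number of NDPP sessions will be available concurrently with each Power-Up cycle.

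**The concern.** Weight change depends on how long a man has been followed. If the first primary weight is taken when the Core ends, and the Core can end at different times, men contribute different lengths of follow-up to the same endpoint. Within an arm this adds noise and blurs what is estimated. Between arms, a difference in mean timing would add to or subtract from the treatment effect.

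The protocol leaves room for such a difference in three ways. Weights are mainly tied to sessions. The control classes are not tied to Power-Up's calendar beyond being concurrent and similar in number. Men who never attend have no end-of-Core date, and the record weights meant to cover them may come from any clinical visit in the year. Hypothesis 2 expects better attendance under Power-Up. If that is right, the mix of session-timed weights and weights of arbitrary date would itself differ by arm.

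**Working it through.** **1. Convert the stated durations.** One month is 365.25 / 12 / 7 = 4.348 weeks.

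- 16 weeks = 16 / 4.348 = 3.7 months.
- 6 months = 6 × 4.348 = 26.1 weeks.
- Spread in the end of the Core = 26.1 − 16 = 10.1 weeks.

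**2. Reproduce the plan's own cycle length.** The Intervention Cycles Timeline gives 10 to 12 months.

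- Core of 16 weeks plus 6 months of maintenance: 3.7 + 6 = 9.7, about 10 months.
- Core of 6 months plus 6 months of maintenance: 6 + 6 = 12 months.

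The stated range is what results when the Core ends anywhere between week 16 and month 6. The 10-week spread is therefore built into the protocol's own figure.

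**3. Check the session counts.** The Core has 16 sessions throughout. Adding 6, 8 or 10 maintenance sessions gives 22, 24 or 26. The stated total of 24 matches only 8. This is a conflict to reconcile, but it does not move the assessment, because the maintenance phase lasts six months in both descriptions.

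**4. The 12-month weight.** Section 1b puts it at the end of 12 months. A cycle that finishes at 10 months ends 2 × 4.348 = 8.7 weeks earlier. A gap arises only if the weight is taken at the final session, as Retention Strategies allows, and not at the calendar date.

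**5. Illustration of size.** The protocol gives no rate of loss, no standard deviation and no difference in timing between arms, so all three are assumed here. The rate is 0.05 to 0.20% of body weight per week, linear and still under way at week 16. The SD of percent change is 4 to 6 points. There are 300 / 2 = 150 men per arm, treated as independent, no true effect, and a two-sided 5% z-test.

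- Bias = rate × difference in mean weighing time.
- SE = SD × √(2/150), which is 0.46, 0.58 and 0.69 points for SD 4, 5 and 6.
- False rejection = 1 − Φ(1.96 − bias/SE) + Φ(−1.96 − bias/SE).

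| Difference in mean timing | Bias (points) | False rejection |
|---|---|---|
| 2 weeks | 0.1 to 0.4 | 5% to 14% |
| 5 weeks | 0.25 to 1.0 | 6.5% to 58% |
| 10.1 weeks | 0.5 to 2.0 | 11% to 99% |

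The last row is a limit, not a forecast. It needs one whole arm weighed at week 16 and the other at month 6.

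**The case against.** The strongest reply is that the protocol means calendar time throughout. It uses a 16-week label repeatedly, a designated group session has a scheduled date whether or not a man has completed every earlier session, and the 6-month allowance may be only an outer limit for make-up sessions. This is a fair reading of the labels. It does not account for the sentence in section 1b that delivers the 16 Core sessions over 6 months, or for an outcome definition that names the end of the Core. The conflict stands.

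A second reply is that windows belong in the statistical analysis plan, which is not shown. That is right for a window's width. The point here is that the protocol states its primary outcome by one clock and its hypothesis by another.

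Four stronger inferences are tempting, and the text does not support them:

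- **That control men start separately and run at another pace.** The protocol does not say so. It describes NDPP sessions as concurrent with each Power-Up cycle, and reminders go out for the same labelled weigh-ins in both arms. It does not guarantee a common calendar either.
- **That the 12-month primary weight is defined by the final maintenance session and carries a one-month window.** The words "goal of +/- 1 month of the 12-month final maintenance session" concern the telephone survey. The outcome definition says the end of 12 months.
- **That men who never attend have no weight.** Home scales, additional collection procedures and record weights are all provided. What those record weights lack is a target date.
- **That the maintenance count shifts the endpoint.** The phase lasts six months under either count.

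**Conclusion.** The concern holds for the first primary weight. Its date is fixed by two rules that can differ by about 10 weeks, and this follows from the protocol's own durations without further assumption.

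That mean timing differs by arm is a possibility the text leaves open, not something it shows. The size of any bias cannot be computed from the protocol. Under the assumed rates and SDs, a 2-week difference ranges from negligible to modest, and a 5-week difference could be as large as 1 point. The 12-month weight is a lesser concern: its definition is calendar time, and only the collection text and the 10-to-12-month cycle pull it away.

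This should be fixed before outcomes are compared by arm. It is not a fatal flaw.

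**What to change.** Define both primary weights as percent change at 16 weeks and at 12 months after one index date that is fixed before allocation and applied identically in both arms. Either randomisation or the scheduled start of the man's cycle would serve. The first includes any wait before classes begin; the second must be recorded before the arm is known. Take the reading nearest the target day within one common window, whatever session the man has reached. Use the connected home scale when no session weight falls in the window, and hold record weights to the same window. The protocol gives no figure from which to choose the window's width, so the investigators should set it without sight of outcomes by arm.

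Replace the end-of-Core wording in the section 1b outcome definition. The investigators should also reconcile the Core duration and the maintenance session counts across the Intervention Cycles Timeline, section 1b and Adverse Event Monitoring. Which schedule is right is for them to say.

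The cost is protocol wording and a date rule in the analysis dataset. No new visits are needed, since men already receive scales. Some session weigh-ins will fall outside the window and be replaced by home-scale readings. Some men will be weighed at 16 weeks before finishing the Core, so the endpoint becomes weight at a fixed time and no longer weight after the full Core, which is what Hypothesis 1 already describes.

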2. ADEQUACY OF PROTECTION AGAINST RISKS

2a. Informed Consent. Study staff who have undergone human subjects training and who are approved by our IRB will obtain oral informed consent from participants by phone, after completing eligibility screening. Because of the nature of the study design, it is not feasible to consent participants in person. Creating a need to attend a study visit outside of attendance of *Power-Up* or NDPP sessions would create a barrier to participation that detracts from our efforts to ensure a generalizable sample that is representative of men who participate in Diabetes Prevention Programs. Obtaining consent at the first intervention session is not practical because it would further distort the sample's representativeness of the population of interest by limiting the sample to those who successfully attend the first session of these interventions. This would also be a threat to internal validity, as it would artificially equate the two interventions on attendance of the first session. Based on our IRB's prior approval of the oral consent procedures for other studies, including the soon to be complete *NYC Care Calls*, conducted in partnership with PCIP/NYC-DOHMH, we are confident that oral consent procedures will be approved for the current study. Our study also meets all of the Federal requirements (45 CFR 46) for waiver of written consent: (i) the research involves no more than minimal risk to the subjects; (ii) the research could not practicably be carried out without the requested waiver or alteration; (iii) the waiver or alteration will not adversely affect the rights and welfare of the subjects; and (iv) whenever appropriate, the subjects or legally authorized representatives will be provided with additional pertinent information after participation.

Oral consent by telephone will include all of the following steps:

- All aspects of the study, as described in the consent form, are first discussed with the potential participant. The consent form is thoroughly reviewed and answers to the potential participant's questions are provided.
- After reviewing the consent form by phone, the staff person obtaining consent will verbally assess the individual's comprehension of the research and what it means to participate, including understanding of the voluntary nature of participating. Individuals will be asked to answer the following questions: (1) What are you being asked to do? (2) What question is this study trying to answer? (3) What are the potential risks of participating in this study? (4) How often will you need to come in for study visits? (5) What is the difference between participating in this study and your standard medical care? (6) What should you do if you decide to withdraw from the study?
- If the participant does not demonstrate sufficient capacity to answer the questions about the study and thus may not be able to provide informed consent, this will be documented and the participant will be excluded from study participation.
- Upon request a copy of the consent information sheet will be mailed or emailed to the participant once enrolled by the study staff. A record of completed oral consent and mailing of the printed consent document, which will include an instruction to call the study offices if the participant has any questions after reading, will be recorded in each individual's study files, which will be stored in a secure location.

Potential participants who do not have capacity to provide consent will be provided with information about how to access the NDPP through talking with their provider who would discuss whether the program may or may not be appropriate for them. Potentially eligible subjects will be invited to participate, consented, randomized to a study arm and either directed to the *Power-Up* intervention coordinator or to the NDPP coordinator at PCIP depending on the patient's health care home. The consent document will include information about study procedures, including that participants will be randomized to either standard NDPP or *Power-Up*, that they will be contacted by telephone, email (if applicable) and mail for follow-up surveys, and the risks and benefits of the intervention. We will ask for permission to leave telephone messages, without identifying the exact purpose of the call, when we are making study-related calls. We will also ask for permission to send text messages via the coaches as reminders for sessions and questionnaires. Participation in the proposed study will be completely voluntary. Prospective subjects will be told that a decision to decline participation will not affect their health care.

The proposed research will follow the Health Insurance Portability and Accountability Act of 1996 (HIPAA) guidelines for protecting the privacy and documenting informed consent of participants. Intervention recruitment, consent, and enrollment will not begin until the study receives approval from the AECOM IRB, as outlined in the Consortium of Informed Consent Section.

Databases will be secured with encryption and use of secure servers. The REDCap data management system is a secure, web-based application designed to support data capture for research studies, providing: 1) an intuitive interface for validated data entry; 2) audit trails for tracking data manipulation and export procedures; 3) automated export procedures for seamless data downloads to common statistical packages; and 4) procedures for importing data from external sources. The REDCap website is password-protected and restricted to users who have been authorized to gain access. The site employs a multi-level authorization structure where certain areas are available to all authorized users and other areas available only to specified users. Within each area there are different levels of authorization related to whether an individual has 'view only' privileges or has 'data entry' privileges. We have access to REDCap without a need to charge the current study's budget through AECOM.

2b. Protection Against Risk. Every effort will be made to prevent a breach of confidentiality. Individuals who enroll in the study will be assigned a unique ID number. All study data will be maintained with the IDs rather than names or identifiable information. *Power-Up* study director will keep a log linking the ID number to identifiable contact information for follow-up purposes. The log will be maintained on a password-protected

directory accessible to the *Power-Up* research staff only.

Data will be collected using 1) hard copy surveys until we finalize the online database (REDCap); and 2) digitally recorded in-person and telephone interviews and focus groups.

- Surveys will be administered primarily over the phone and occasionally in person (when pursuing missing data) by the study staff. Data will be entered from hard copies into the confidential study database by the study staff.
- Interviews and focus groups will be facilitated by the study staff and/or graduate students and post-doctoral fellows in Clinical Health Psychology, working in [name] research lab; they will be audio recorded using a digital recorder. Interview recordings will serve as backup to notes. Focus group recordings will be professionally transcribed. Recordings and typed transcripts will be transmitted via the secure FTP server. The transcriber will sign a confidentiality agreement, attesting to the fact that data in the recordings will remain private. These qualitative interviews and focus groups, administered after participation in the main study activities, will utilize a consenting process that is separate from and supplementary to the process for the main study, and will be completely voluntary.
- The study staff will ask the study participants to only use their first name when they joining a virtual sessions, suggest to turn off their camera, and ensure that the virtual sessions are not recorded. If the participant is joining via phone, the staff will ask them to join privately. If the participant chooses not to follow these instructions, they will be expose to potential security risks.

Hard copy documents, including locator forms and surveys, will be stored in locked file cabinets at AECOM, accessible only to the *Power-Up* research team. Forms with identifying information (e.g. consents) will be stored in a different cabinet from the completed surveys and any other study data. All electronic data will be stored at AECOM on password-protected drives that are backed up daily. Hard copy and electronic data will be accessible to study staff only.

After data collection is complete, the research team will agree on the parameters for de-identifying this data (e.g. choosing among top or bottom coding, adding random noise, stochastic data interchanges, or other methods) to adequately protect participants' confidentiality. The de-identified demographics file, linked to the survey results and weight and activity tracker will be used by the *Power-Up* data analyst for specific preliminary and final analyses.

Provisions for ensuring necessary medical or professional intervention in the event of adverse effects will be coordinated through [name], but will follow usual PCIP procedures. Adverse events reported directly by lifestyle coaches will be referred directly to [name]. He will also monitor the de-identified data collected on an ongoing basis to ensure the safety of subjects enrolled in our study. We feel that these measures are adequate to protect against risk.

Expression of intent to harm self and/or others. Subject will be informed during consenting about the limits to confidentiality if intent to harm self and/or others is expressed. Study staff shall assess a subject's expression of harming self and/or others. Harm deemed imminent shall be immediately reported to the local authorities as required by state law. Staff will note alert in chart and notify the subject's primary care provider. Intent to harm self and/or others shall be recorded as a Serious Adverse Event at the local and coordinating center IRB. Because surveys will primarily be conducted by phone, we will use the PHQ-8 scale to assess depressive symptoms (See Table 1, Research Strategy), rather than the PHQ-9, to avoid directly inquiring about suicidal risk. Given the target population, true imminent suicidal risk is expected to be exceedingly rare and asking questions about suicidal ideation would mostly yield false positives. However, all staff will be trained in suicidal risk assessment by [name], a licensed clinical psychologist in NY State, and will be trained in a protocol of how to respond to risk with referrals for mental health care at one end of the spectrum of risk and calling 911 and/or crisis response teams at the other.

Breach of confidentiality. Study participants face risks related to inadvertent release of confidential information.

This will be minimized through careful adherence to best practices for data collection and management. All research staff will be trained in principles and methods for assuring participant confidentiality and safety. Efforts, such as keeping research records secure and allowing only authorized people to have access to research records, will be made to keep the information safe. Participants will be given any new information we become aware of that would affect their willingness to continue to participate in the study.

Data will be used only in aggregate and no identifying characteristics of individuals will be published or presented. Results of assessments will be sent to participants' care providers only if participants agree to this. Confidentiality of data will be maintained by using research identification numbers that uniquely identify each individual. Safeguards will be established to ensure the security and privacy of participants' study records. Databases will not use participants' names as identifiers: a research ID number will be used. The research records will be kept in a locked room in the study offices. The files matching participants' names and demographic information with research ID numbers will be kept in REDCap with restricted access. Only study personnel will have access to these files, and they will be asked to sign a document that they agree to maintain the confidentiality of the information. After the study is completed, data will be stored with other completed research studies in a secured storage vault.

Consent will cover the use of confidential data collected by the study and will permit sharing these data among, incorporation in the study databases, and the distribution of de-identified data for public use databases. If required, an NIH Certificate of Confidentiality will be sought prior to beginning of recruitment to offer further protection of privacy. Limits to confidentiality as it relates to expression of intent to harm self and/or others shall be included in the informed consent.

